## **7.7 Serious Adverse Event Collection and Reporting**

Following the subject's written consent to participate in the study, all SAEs, whether related or not related to study drug, must be collected, including those thought to be associated with protocol-specified procedures. All SAEs must be collected that occur within 30 days of discontinuation of dosing.

All SAEs must be collected that occur during the screening period. If applicable, SAEs must be collected that relate to any protocol-specified procedure (e.g., a follow-up skin biopsy). The

investigator should report any SAE that occurs after these time periods that is believed to be related to study drug or protocol-specified procedure.

### **7.8 Expedited Adverse Event Reporting to Overall PI**

Investigators **must** report to the Overall PI any serious adverse event (SAE) that occurs after the initial dose of study treatment, during treatment, or within 30 days of the last dose of treatment on the local institutional SAE form.

Investigators will report AEs directly to the DFCI Office for Human Research Studies (OHRS) per the DFCI IRB reporting policy, using the local institutional SAE form.

### **7.9 Expedited Adverse Event Reporting to the Food and Drug Administration (FDA)**

The Overall PI, as study sponsor, will be responsible for all communications with the FDA. The Overall PI will report to the FDA, regardless of the site of occurrence, any serious adverse event that meets the FDA's criteria for expedited reporting following the reporting requirements and timelines set by the FDA.

SAEs should be reported on MedWatch Form 3500A, which can be accessed at: <http://www.accessdata.fda.gov/scripts/medwatch/>.

MedWatch SAE forms should be sent to the FDA at:  
MEDWATCH

### **7.10 Expedited Adverse Event Reporting to Hospital Risk Management**

Participating investigators will report to their local Risk Management office any participant safety reports or sentinel events that require reporting according to institutional policy.

### **7.11 Expedited Adverse Event Reporting to BMS**

SAEs, whether related or not related to study drug, and pregnancies must be reported to BMS within 24 hours. SAEs must be recorded on BMS or an approved form; pregnancies on a Pregnancy Surveillance Form.

If only limited information is initially available, follow-up reports are required. (Note: Follow-up SAE reports should include the same investigator term(s) initially reported.)

If an ongoing SAE changes in its intensity or relationship to study drug or if new information becomes available, a follow-up SAE report should be sent within 24 hours to the BMS (or designee) using the same procedure used for transmitting the initial SAE report. All SAEs should be followed to resolution or stabilization.

---

CONFIDENTIAL

*This document is confidential. Do not disclose or use except as authorized.*

IRB APPROVED

The Sponsor/Investigator will ensure that all SAEs in the clinical database are reported to BMS and any applicable health authority during the conduct of the study. This reconciliation will occur at least quarterly and be initiated by the sponsor/investigator. Sponsor/investigator will request a reconciliation report from: . During reconciliation, any events found to not be reported previously to BMS must be sent to

BMS will be provided with a simultaneous copy of all adverse events filed with the FDA.

All SAEs should simultaneously be faxed or e-mailed to BMS at:  
Global Pharmacovigilance & Epidemiology  
Bristol-Myers Squibb Company

## 8. PHARMACEUTICAL INFORMATION

A list of the adverse events and potential risks associated with the investigational agents administered in this study can be found in the Investigator's Brochures and/or Package Inserts.

### 8.1 IND Agents

#### 8.1.1 Description

**Product information table: please also see respective product investigator brochures**

Table Product Description					
Product Description and Dosage Form	Potency	Primary Packaging (Volume)/Label Type	Secondary Packaging (Qty) /Label Type	Appearance	Storage Conditions (per label)
Nivolumab BMS-936558-01 Solution for Injection*	100 mg (10 mg/mL)	10 mL vial	5 vials per carton/ Open-label	Clear to opalescent colorless to pale yellow liquid. May contain particles	2 to 8°C. Protect from light and freezing
Ipilimumab Solution for Injection	200 mg (5 mg/mL)	40 mL vial	4 vials per carton/Open-label	Clear, colorless to pale yellow liquid. May contain particles	2 to 8°C. Protect from light and freezing.

\*Nivolumab may be labeled as bms-936558-01 solution for injection

### **8.1.2 Storage and Stability**

If stored in a glass front refrigerator, vials should be stored in the carton. Recommended safety measures for preparation and handling of nivolumab and ipilimumab include laboratory coats and gloves.

For additional details on prepared drug storage and use time of nivolumab or ipilimumab under room temperature/light and refrigeration, please refer to the bms-936558 (nivolumab) and ipilimumab investigator brochure section for “recommended storage and use conditions” and in Appendix C.

### **8.1.3 Handling**

Qualified personnel, familiar with procedures that minimize undue exposure to themselves and the environment, should undertake the preparation, handling, and safe disposal of the chemotherapeutic agent in a self-contained and protective environment.

### **8.1.4 Availability**

Free of cost, investigational supply of nivolumab and ipilimumab will be provided by Bristol-Myers Squibb.

### **8.1.5 Ordering**

Dana-Farber Research Pharmacy will request supply of nivolumab and ipilimumab from Bristol-Myers Squibb by submitting the order form.

### **8.1.6 Accountability**

Accountability for investigational agents at the study site is the responsibility of the sponsor-investigator. Study drug will be dispensed only to eligible patients by Dana-Farber Research Pharmacy. The appropriate study personnel will maintain records of study drug receipt and dispensing at Dana-Farber Research Pharmacy. A careful record of the inventory and disposition of the agent will be maintained, using the NCI Drug Accountability Record Form (DARF).

### **8.1.7 Destruction and Return**

Unused supplies and expired supplies of the investigational agents will be destroyed on site, by the Dana-Farber Research Pharmacy.

## **9. BIOMARKER, CORRELATIVE, AND SPECIAL STUDIES**

### **9.1 Biomarker Studies**

Patients will be asked to provide mandatory blood samples at several time points as specified in the study calendar. Strongly recommended sequential biopsies, if safely accessible, at specified

---

*CONFIDENTIAL*

*This document is confidential. Do not disclose or use except as authorized.*

**IRB APPROVED**

time points will provide fresh tumor samples for analysis.

Correlative blood samples will be drawn prior to treatment, at 2 weeks after start with either nivolumab or ipilimumab (end of week 2, prior to week 3) at week 9, and at 6 and 12 months after start of protocol treatment, and at the time of treatment discontinuation (or within 30 days after). Cell-free DNA will be analyzed using NexGen sequencing to detect the presence and changes in the amount of cell free DNA (cfDNA). Flow-based cell sorting will be used to determine if circulating tumor cells are present and how the proportion of CD4, CD8, and Treg cells changes over the course of treatment. These changes will be correlated with clinical response. We will also profile T cell neoantigens.

Blood collection tubes as specified below will be obtained at the time points indicated in the study table. There is a +/- 3 day window (for obtaining these samples except for collection at W2 prior to start of second drug). These collections will be taken at the time of routine blood collection time points required for this study. Specimens will be processed on site according to instructions below and shipped (via traceable carrier) to Dana-Farber Cancer Institute. Once the shipment is received, samples will be subsequently processed, analyzed, and stored at Dana-Farber Cancer Institute.

All tubes should be transported at (ambient) room temperature. Collection kits containing the appropriate tubes will be sent to participating sites.

Sequential biopsies are strongly recommended for patients with accessible tumor. These will consist of core needle biopsies and if necessary open biopsies.

Samples will be subject to immune cell analysis by flow cytometry as previously described. Live cells will be used for in vitro analysis of immune response in the organotypic tumor spheroid culture system in either the lab of [name] or the [name] lab where response to nivolumab and ipilimumab will be determined. The responses seen in vitro will be correlated with clinical response. Biopsies may be obtained prior to treatment start, after 2 weeks of treatment with one drug alone, following restaging CT scans at 8 weeks (within a 10 day window) and at time of progression.

TIL's will undergo RNA sequencing to determine changes of expression in response to nivolumab, ipilimumab or both drugs combined. This will allow to identify antigens involved in immune response as well as resistance mechanisms that could account for primary or secondary resistance and tumor progression.

The tissue will be used to assess PD-1, PDL-1 expression, T-cell infiltration on IHC and flow cytometry.

Whole exome sequencing (WES) and RNA sequencing to assess changes in expression profile will be performed. Single cell sequencing of infiltrating immune cells will be performed as well.

Tissue will be stained for STING protein expression.

These studies will provide information that will help to identify patterns indicative of response and resistance to immunotherapy with nivolumab and ipilimumab in thyroid cancer.

As additional hypotheses about the drivers of response and resistance arise over the course of the study, investigators may choose to use additional tissue testing methodologies beyond those laid out above. Investigators may also request additional archival tissue for such testing.

Non-DF/HCC sites will be responsible for shipping samples via overnight delivery to DF/HCC on the day of collection. DF/HCC will provide shipment instructions to participating sites. This applies only to biomarker samples (routine laboratory samples will be analyzed locally).

## 10. STUDY CALENDAR

Baseline evaluations are to be conducted within 3 weeks prior to study registration. If these screening assessments occur within 3 days before start of study treatment, then they may serve as the baseline cycle 1 day 1 values and do not need to be repeated. Each treatment cycle will be 6 weeks long. Scans must be done  $\leq$ 4 weeks prior to study registration.

As detailed in the Study Calendar, a negative pregnancy test in women of child-bearing potential must be documented within 24 hours of the first dose of study drug.

Laboratory evaluations do not need to be repeated to meet eligibility criteria on date of first treatment dose, if they were done within 3 days of the first treatment dose.

In the event that the participant's condition is deteriorating, laboratory evaluations should be repeated within 48 hours prior to initiation of the next treatment dose.

Assessments must be performed prior to administration of any study agent. Study assessments and agents should be administered within  $\pm$  3 days of the protocol-specified date, unless otherwise noted.

	Screening	Week 1	Week 3	Week 5	Week 7	Week 9	Week 11 and Beyond h	End of Treatment h	Follow up visit 30 (+/-7) days after the last dose
Informed consent	X								
Medical History	X								
ECG	X							X i	
B-HCG (WOCBP only) a	X	X			X			X	

Physical exam (Ht, Wt, VS, PS) b	X	X	X	X	X	X	X	X	X
Performance Status	X	X	X	X	X	X	X	X	X
Routine labs c	X	X	X	X	X	X	X	X	X
Tumor Markers d	X				X				
Adverse event evaluation						X			
Radiologic evaluation e	X					X			
Correlative blood collection	X i		X i			X i		X i	
Correlative tissue collection	X f		X g			X g			
Nivolumab		Every 2 weeks for a maximum of 24 months (starting on week 1 in arms 1 and 3 and in week 3 in arm 2)							
Ipilimumab		Every 6 weeks for a maximum of 24 months (starting on week 3 in arm 1 and week 1 in arms 2 and 3)							

- a) Serum or urine at screening and at day 1 of each cycle
- b) Physical exam is symptom directed. Height measured at screening only
- c) Routine labs include: CBC w/differential, Chemistry panel including: Albumin, LDH, AST, ALT, ALP, T.Bili, BUN or serum urea level, creatinine, Ca, Mg, Na, K, Cl, phosphate, glucose, amylase, lipase, TSH, Free T4. TSH and Free T4 are only required at screening and then at day 1 of each cycle starting with cycle 2.
- d) At each cycle, collect Serum calcitonin, CEA (carcinoembryonic antigen), and CA19-9 for MTC, and Thyroglobulin antibodies (TgAb), and thyroglobulin (Tg) for DTC.
- e) Scans every 8 weeks during protocol therapy, or as clinically indicated
- f) Fresh biopsy or archival tissue
- g) Fresh biopsy is strongly recommended (if safe to perform), at weeks 3 and 9 and at treatment discontinuation
- h) Participants will be followed for response until treatment discontinuation or disease progression (whichever comes last) and for survival for 2 years from study registration. Post end of protocol treatment, if first disease progression has not been confirmed, tumor assessments are to continue every 3 months (+/- 1 month) until first disease progression, death, or 2 years post study registration. After first disease progression has been confirmed, patients will be followed for survival by phone only, every 3 months (+/- 1 month) until death or 2 years post study registration, whichever occurs first
- i) Correlative blood samples will be collected at screening (any time after consent and before week 1 treatment) then during treatment at week 3, week 9; after 6 and 12 months of start of treatment; and following treatment discontinuation (EOT sample can be collected on the day of EOT visit or within 30 days afterwards)
- j) EOT ECG can occur on the day of EOT visit or within 30 days afterwards

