Data are emerging about checkpoint inhibition in thyroid cancer. PD-1 and PD-L1 expression has been documented and expression appears to be more pronounced in more advanced cases (Han and Walfish, ATA 2015). If the BRAF V600E mutation is present, which occurs in approximately 60% of newly diagnosed cases of DTC, PDL-1 expression and tumor infiltrating lymphocytes appear to be higher than in BRAF-V600E no-mutated (WT) cases (40). Pembrolizumab, was tested in extensive phase 1 studies which included a number of RAI refractory thyroid cancer cases and PR's occurred in 2/22 (9%) cases that were PD-L1 positive. These data were presented at the annual ASCO meeting 2016.

The lack of predictive markers that could be used to select patients is a challenge in immunotherapy research. The correlation between PD-1 and PDL-1 expression and response to checkpoint inhibition is weak and of limited clinical usefulness in many tumor types. Traditional cell culture and tumor transplant models do not reflect the immune microenvironment and are also not considered reliable to predict tumor response *in vivo*.

Scientists at MIT and Dana Farber have developed a unique microfluidic chamber which allows the growth of tumor spheroids while preserving the full array of tumor invading immune cells. We have found that spheroids grown from 3 patients with RAI refractory thyroid cancer (2 RAI refractory papillary TC, one Hurthle cell follicular TC) showed mild response to PD-1 inhibition but a dramatic and very rapid response to CTLA-4 inhibition. Cytokine measurements in the cell culture fluid showed a rise in TNF-alpha, IL6, IFN gamma and IL2, all indicating response to checkpoint inhibition with CTLA-4 which closely resembles what would be expected *in vivo* (41). Of note, all patients had recently or currently been treated with mTOR inhibitors.

We recently treated a patient with anaplastic thyroid cancer off label with nivolumab and saw a mixed response with some lesions growing while others were getting smaller.

At this point, no standard options exist for patients with RAI refractory thyroid cancer or medullary thyroid cancer beyond first line treatment. Since none of the treatments available are curative and induce responses for limited time only, there is a major unmet need for treatment options.

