### **3.2 Exclusion Criteria**

1. Patients should be excluded if they have an active, known or suspected autoimmune disease. Subjects are permitted to enroll if they have vitiligo, type I diabetes mellitus, residual hypothyroidism due to autoimmune condition only requiring hormone replacement, psoriasis not requiring systemic treatment, or conditions not expected to recur in the absence of an external trigger
2. Diagnosed or treated for another malignancy within 2 years before administration of the first dose of study drug, or previously diagnosed with another malignancy and have any evidence of residual disease. Patients with nonmelanoma skin cancer or carcinoma in situ of any type are not excluded if they have undergone complete resection.
3. Patients should be excluded if they have a condition requiring systemic treatment with either corticosteroids ( $> 10$  mg daily prednisone equivalents) or other immunosuppressive medications within 14 days of study drug administration. Inhaled or topical steroids and adrenal replacement doses  $> 10$  mg daily prednisone equivalents are permitted in the absence of active autoimmune disease.
4. As there is potential for hepatic toxicity with nivolumab or nivolumab/ipilimumab combinations, drugs with a predisposition to hepatotoxicity should be used with caution in patients treated with nivolumab-containing regimen.
5. Patients who have had chemotherapy/radiotherapy and/or targeted agents within 2 weeks (6 weeks for nitrosoureas or mitomycin C) prior to entering the study or those who have not recovered from adverse events due to agents administered more than 4 weeks earlier. For patients with anaplastic thyroid cancer or otherwise particularly aggressive disease (as determined by the investigator), the washout period for chemotherapy/radiotherapy and/or targeted agents will be at the investigator's discretion.
6. Patients who are receiving any other investigational agents.
7. Patients with active brain metastases should be excluded from this clinical trial because of their poor prognosis and because they often develop progressive neurologic dysfunction that would confound the evaluation of neurologic and other adverse events.
8. Uncontrolled intercurrent illness including, but not limited to, ongoing or active infection, symptomatic congestive heart failure, unstable angina pectoris, cardiac arrhythmia, or psychiatric illness/social situations that would limit compliance with study requirements.

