## 5.2 Pre-Treatment Criteria

Eligibility and exclusion criteria are provided in Section 3. These criteria will be assessed 21 days prior to study registration to establish eligibility and baseline values.

Informed consent will be obtained after the study has been fully explained to the subject and before the conduct of any screening procedures or assessments. If screening assessments occur within 3 days before start of study treatment, then they may serve as the baseline cycle 1 day 1 visit and cycle 1 day 1 labs do not need to be performed.

Demographic information and baseline characteristics will be collected at the Screening Visit. Standard demographic parameters include age, sex, and race/ethnicity (recorded in accordance with prevailing regulations). Baseline characteristics will include ECOG PS (Appendix A), disease status, medical histories, and prior and concomitant medications.

Additional testing required, as per Section 3, is: hematology panel (see Table 1), chemistry panel (see Table 1), coagulation panel, urine or serum HCG (in women of childbearing potential; see Section 3 for when serum HCG testing is required), TSH (with reflexive Free T4 and Free T3), Mg, LDH, amylase, lipase.

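### The only baseline correlative blood may be drawn before prior-drug washouts are finished, which can bias the exploratory change from baseline that the lead-in is meant to supply

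*Combined protocol and SAP*

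**What the plan says.** **Timing of the baseline blood.** Section 10, footnote i: "Correlative blood samples will be collected at screening (any time after consent and before week 1 treatment". Section 9.1 is no tighter: "Correlative blood samples will be drawn prior to treatment, at 2 weeks after start with either nivolumab or ipilimumab". The calendar marks correlative blood at screening, week 3 and week 9, with later draws in footnote i. There is none at week 1.

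**When screening opens.** Section 5.2 places consent "before the conduct of any screening procedures or assessments". Section 10: "Baseline evaluations are to be conducted within 3 weeks prior to study registration".

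**Washouts.** Section 3.2, exclusion 5, bars "chemotherapy/radiotherapy and/or targeted agents within 2 weeks (6 weeks for nitrosoureas or mitomycin C) prior to entering the study". For anaplastic or otherwise particularly aggressive disease it leaves this washout to the investigator. Exclusion 3 bars systemic steroids above 10 mg prednisone equivalent or "other immunosuppressive medications within 14 days of study drug administration"; section 6.8.2 repeats the 14 days, counted from first treatment.

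**Use of the samples.** Sections 2.4 and 13 give the purpose of the randomised lead-in as studying the immune changes caused by each drug alone and by both together. Section 13 plans within-subject marker change and states 82% power for a 0.54 SD mean change in 32 DTC patients (Wilcoxon signed-rank, two-sided 0.05). It calls these studies exploratory.

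**The concern.** The lead-in gives each randomised patient two weeks on one checkpoint drug. For that period, the within-arm estimate of a single drug's effect is the week 3 value minus the baseline value. It has that meaning only if nothing else relevant changed between the two draws.

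Neither footnote i nor section 9.1 ties the baseline draw to the end of a washout. If the sample is taken while the patient is on a kinase or mTOR inhibitor or systemic steroids, or has only just stopped, the change to week 3 includes any effect of stopping that drug. The measures named in section 9.1 include CD4, CD8 and Treg proportions and cell-free DNA. No planned analysis takes account of the timing of prior therapy.

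The plan is stricter elsewhere. Screening assessments reused as cycle 1 day 1 values must fall within 3 days before treatment starts, and section 9.1 excepts the draw before the second drug from its ±3 day window. The immune baseline has no comparable limit, and it cannot be collected again once treatment has begun.

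**Working it through.** **1. Timeline**

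Let day 0 be registration and *g* the days from registration to first dose. The documents state no maximum for *g*. Assume that the 3-week screening window also applies to the correlative blood; footnote i itself limits it only by consent.

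- Earliest baseline draw: day −21.
- Targeted agents, reading study entry as registration: must have stopped by day −14. A draw from day −21 to day −14 (21 − 14 = 7 days) can be on drug. A later draw can fall inside an unfinished washout.
- Steroids and immunosuppressants, counted from dosing: must have stopped by day *g* − 14. Days open to an on-drug draw: 21 − (14 − *g*) = 7 + *g*.
- Baseline to the week 3 sample: 21 + *g* + 14 = 35 + *g* days at most, against 14 if the baseline is drawn on the day of first dose.

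**2. The plan's own power figure**

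Inputs from section 13: n = 32, mean change 0.54 SD, signed-rank test, two-sided 0.05. The signed-rank efficiency under normality is 3/π, so the effective n is 32 × 3/π = 30.6 and the noncentrality is 0.54 × √30.6 = 2.99. The noncentral t gives 82.3%. Simulation with the exact signed-rank null (critical value 159, exact alpha 0.0498, 100,000 runs) gives 82.7%. The stated 82% is reproduced. It assumes that no change comes from any source other than the study drugs.

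**3. What a drift would do**

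Every drift size and share below is an assumption. The documents supply none. Same exact test, n = 32, by simulation.

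No checkpoint effect:

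| Mean drift over all patients | False-positive rate |
|---|---|
| 0 | 5% |
| 0.1 SD | 8% |
| 0.2 SD | 19% |
| 0.3 SD | 36% |

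No checkpoint effect, only some patients shifted:

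| Share shifted | Shift | False-positive rate |
|---|---|---|
| 25% | 0.5 SD | 10% |
| 50% | 0.5 SD | 26% |
| 50% | 1 SD | 66% |

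True effect 0.54 SD, drift in the opposite direction:

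| Opposite mean drift | Power |
|---|---|
| 0.1 SD | 66% |
| 0.2 SD | 45% |
| 0.3 SD | 25% |

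**4. What leaving out affected patients would cost**

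Suppose 10% to 30% of the 32 are affected (assumption): 3.2 to 9.6, or about 3 to 10 patients. With the method of step 2, n = 29 gives 78% and n = 22 gives 65%.

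**The case against.** Several points on the other side stand.

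- **Scope.** The correlatives are exploratory. Response, PFS, OS and safety do not use these samples. An Arm 1 versus Arm 2 comparison of change has the same expected washout drift in both arms because of randomisation, and the week 3 to week 9 change does not use the baseline. Only change from baseline within an arm is exposed.
- **Undefined anchor.** Exclusion 5 does not define study entry. Section 13 speaks of patients being entered into arms, which supports registration. If consent were meant, the targeted-agent route would close outside the discretionary exception. The steroid route would remain, because it is counted from dosing.
- **Permission is not frequency.** The schedule allows such a sample; nothing shows that it is common or that it shifts a marker.

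A reader might also infer more than the documents support:

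- *That the DTC cohort is largely TKI-exposed.* Section 3.1 requires progression within 13 months, not progression on a TKI, and offers TKI intolerance or unsuitability as alternatives. Only suitable patients over 65 must have had a prior TKI line, with no recency condition. Prior exposure is also not use at the draw.
- *That section 13 sized the trial on these markers.* The 32 come from the Simon design. Section 13 states the power that this number gives for an unspecified post-baseline value.
- *That the two effects can never be separated.* Section 5.2 collects prior and concomitant medications, so affected samples may be identifiable if stop dates are recorded.
- *That the mTOR remark shows the problem in trial patients.* Section 2.3 says that "all patients had recently or currently been treated with mTOR inhibitors", but this concerns three donors of ex vivo spheroids, not participants' blood.

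**Conclusion.** The point holds as a gap in sampling rules. A fully compliant baseline can be drawn up to 21 days before registration, while the patient is on or coming off a targeted agent, systemic steroids or immunosuppressants. The interval to week 3 can then be 35 days or more instead of 14. For steroids and immunosuppressants this follows from the text, given a 21-day window for the draw. For targeted agents it also needs study entry to mean registration, or the discretionary exception to apply.

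The consequence is possible bias in the exploratory within-arm change from baseline. Its size is unknown: the share of patients affected and any withdrawal effect are not in the documents, so the error rates and power losses above are illustrations. The stated 82% is correctly computed for its assumptions, and the primary analysis is not in question. The change is worth making because it is cheap and the within-arm contrast is part of what the lead-in was set up to provide.

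**What to change.** **Protocol text.** Amend section 10, footnote i, and section 9.1 so that, in all three arms, the baseline correlative blood is drawn pre-dose at week 1, or within 3 days before first dose, the window that section 10 already uses for screening assessments. The baseline to week 3 interval then becomes 14 to 17 days, apart from visit windows. No washout rule needs to change, and no patient is left without a defined baseline, including those whose washout is at the investigator's discretion.

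**Data.** Record the last-dose dates of prior anticancer agents and of systemic steroids or immunosuppressants, and the date of the baseline draw.

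**Samples already drawn earlier.** Keep them in the main analysis. Add a sensitivity analysis that omits baselines taken on, or within 14 days of, those drugs.

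**Cost.** The tubes and the number of draws stay the same, and routine labs are already taken at week 1. Sites lose some flexibility in collection and shipping. The sensitivity analysis has less power: about 78% to 65% if 3 to 10 of 32 patients are omitted (assumed range). For that reason it should not replace the main analysis. A pre-dose draw reduces carry-over but may not remove it, since the patient may be only two weeks off the earlier drug; the recorded dates let the report say so.
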